#### Number of Product Applications

The number of product applications will be summarized for each treatment group in each arm. The difference in mean number of applications between the treatment group and control group will be calculated for each timepoint. Product applications will be defined as the number of product applications prior to complete wound closure within the treatment period for each study arm.

#### **7.6.3. Tertiary Endpoints**

The following tertiary endpoints will be summarized for exploratory purposes. Continuous variables will be summarized using descriptive statistics (number of patients, mean, median, quartiles, standard deviation [SD], minimum, and maximum). Categorical variables will be summarized using frequencies and percentages of patients in each category. Statistical testing may be performed at the request of the sponsor / investigator. Where possible, results will be summarized at each collected time point and the change from baseline will be presented.

#### Quality of Life – SF-36

Results will be summarized at each time point using the proportion of patients at each level. Change from baseline will be assessed as the number of levels either improved or worsened.

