#### **Tertiary Outcome Measures:**

- Quality of Life (SF-36)  
Day of initial application and at either 12 weeks or at complete re-epithelialization (whichever occurs first).

- Incidence of adverse events
- Cost effectiveness / Economic model (amount of product usage, length of treatment)

The following information will be provided for each subject:

- CPT Codes
- HCPCS Codes
- ICD-10 codes
- DRGs (if applicable)
- Dates of Service/Range of service
- Place of Service
- Bill type (131, etc.)

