**Notes:**

- X – Requirement must be completed by study personnel
- (1) – Treatment period visits will cease after complete wound re-epithelialization is confirmed
- (2) – An in-person visit two weeks (± 3 days) after complete wound re-epithelialization is first identified after Week 0 are required for patients with complete wound re-epithelialization. These visits are NOT required if there is not complete wound re-epithelialization at or before 12 weeks.
- (3) – HbA1c and a vascularization assessment can be completed anytime within 60 days prior to Week 0
- (4) – SF-36 Questionnaire and Pain Scale will be completed during the visit when complete wound re-epithelialization is first identified or at 12 weeks (whichever occurs first)

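### The SF-36 is analysed as shifts in levels the plan never defines; named scores with a baseline-adjusted between-arm difference would get more from the same two questionnaires

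*Combined protocol and SAP*

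**What the plan says.** The SF-36 is the first tertiary outcome in Sections 1 and 3. Section 7.6.3 contains all of its analysis text, in two sentences. For each time point: "Results will be summarized at each time point using the proportion of patients at each level". For change: "Change from baseline will be assessed as the number of levels either improved or worsened".

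The opening paragraph of 7.6.3 covers all tertiary endpoints. It calls them exploratory ("The following tertiary endpoints will be summarized for exploratory purposes"), lists the usual descriptive statistics for continuous variables, and adds: "Where possible, results will be summarized at each collected time point and the change from baseline will be presented". Testing is optional: "Statistical testing may be performed at the request of the sponsor / investigator".

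Each patient completes the questionnaire twice. The first is on the day of initial application. For the second, note 4 to the Appendix A schedule says: "SF-36 Questionnaire and Pain Scale will be completed during the visit when complete wound re-epithelialization is first identified or at 12 weeks", whichever comes first. Section 5.12 lists quality of life among the follow-up assessments, but only as the schedule indicates, and the schedule shows these two occasions.

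**The concern.** Three things are missing from the SF-36 rule.

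- **A definition of level.** No section gives categories, cut points or the unit to which a level applies, and none describes scoring. Two analysts could build different tables from the same data, and both would comply.
- **A comparison between arms.** Section 7.6.2 provides a treatment-minus-control difference for wound area, for closure and for number of applications. The SF-36 paragraph has none, and neither does the general tertiary paragraph.
- **Covariate adjustment for Week 0.** The Week 0 questionnaire serves as the reference for change, but no analysis adjusts for it.

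What is at stake is how informative and how well fixed in advance one named outcome is. Moving from scores to a count of levels loses detail. Because testing is available on request, undefined levels also leave room to choose the grouping after the data are seen.

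**Working it through.** The plan states no SF-36 effect, standard deviation, correlation or power, so there is no figure to reproduce. The check has three parts.

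**1. Gain from baseline adjustment, against unadjusted change**

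The comparator is change from baseline, because that is what the plan uses. Assume a numeric score with the same variance σ² at both times and correlation r between them. Then, per patient:

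- raw change has variance 2σ²(1 − r);
- the final score adjusted for Week 0 (ANCOVA) has variance σ²(1 − r²);
- the ratio is (1 − r²) / [2(1 − r)] = (1 + r)/2.

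| r (assumed) | Change, 2(1 − r) | Adjusted, 1 − r² | Ratio | Variance saved |
|---|---|---|---|---|
| 0.3 | 1.40 | 0.91 | 0.65 | 35% |
| 0.5 | 1.00 | 0.75 | 0.75 | 25% |
| 0.7 | 0.60 | 0.51 | 0.85 | 15% |

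Interval width scales with the square root of the ratio: √0.65 = 0.81, √0.75 = 0.87 and √0.85 = 0.92. Intervals are therefore about 19%, 13% and 8% narrower. The gain shrinks as the correlation rises.

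**2. Loss from counting levels (illustration only)**

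This loss depends on levels that the plan does not define. To see its direction, 20,000 trials per setting were simulated with 24 patients per arm (Section 3), normal scores, an assumed effect of 0.8 SD and a two-sided 0.05 test. Levels were taken as equal-probability groups of the score. Power was:

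| r (assumed) | Adjusted score | Raw change | Change in 5 levels | Change in 3 levels |
|---|---|---|---|---|
| 0.3 | 0.80 | 0.63 | 0.53 | 0.46 |
| 0.5 | 0.87 | 0.77 | 0.64 | 0.55 |
| 0.7 | 0.97 | 0.94 | 0.82 | 0.70 |

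The order was the same in every setting tried, including an effect of 0.5 SD and 20 patients per arm. The sizes belong to these assumptions and are not estimates for this trial.

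**3. Timing of the second questionnaire**

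Healed patients answer at the visit where closure is first seen, and the others at Week 12. Section 7.3 assumes closure in 80% and 40%. With 24 per arm, 0.80 × 24 = 19.2 and 0.40 × 24 = 9.6, so about 19 and 10 patients would answer at closure. Section 2.1 gives a mean time to closure of 6.4 weeks in the single-arm pilot. On the plan's own assumptions, the arms would therefore tend to answer at different times. Adjusting for Week 0 does nothing about that.

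**The case against.** The strongest defence is that the endpoint is tertiary and descriptive, with no hypothesis, alpha or sample size attached, so precision carries little weight. The opening paragraph of 7.6.3 already provides means, standard deviations and change from baseline for continuous variables. Nothing in the SF-36 paragraph says this no longer applies, so level shifts could be an additional summary. On that view, the plan needs only a definition of level.

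Much of this stands. It limits the weight of the point and rules out several stronger readings that a reader might infer:

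- **That the SF-36 paragraph overrides the general rule.** The text does not say so. The two can be read together, though they leave the choice open.
- **That levels are item responses, giving many sparse tables.** The plan never ties levels to items. They could be bands of a scale or summary score.
- **That the Week 0 questionnaire goes unused.** It is the reference for change. Only covariate adjustment is absent.
- **That adjustment saves 25% of variance at r = 0.5 and 49% at r = 0.7.** Those are r², the saving against an unadjusted final score, which is not the planned analysis. Against change, the saving at r = 0.7 is 15%.

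What does not stand is that the general paragraph settles the matter. Even on the generous reading, it names no SF-36 score, gives no between-arm difference or interval, and leaves level undefined. Section 7.8 mentions a formal statistical analysis plan, but only for further imputation variables. Nothing shows that it defines SF-36 levels.

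**Conclusion.** The point holds as a low-cost improvement to an exploratory endpoint. That levels and scoring are undefined rests on the documents alone. The gain from adjustment assumes that numeric scores will be derived, with similar variance at both times. On that basis it is 35%, 25% and 15% of variance at r = 0.3, 0.5 and 0.7, relative to unadjusted change. Grouping a score into levels costs something more, but the amount cannot be computed from the documents.

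Two limits apply. The primary and secondary conclusions are unaffected. And an adjusted difference would compare quality of life at the end of each patient's treatment period, not at a common time, because the second assessment depends on healing.

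**What to change.** Rewrite the SF-36 paragraph of Section 7.6.3 to:

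1. name the SF-36 scores to be reported and the scoring method, and say how a missing second questionnaire is handled;
2. report mean change from Week 0 by arm for each named score;
3. give a between-arm difference with a confidence interval, adjusted for the Week 0 score and labelled exploratory;
4. define any level summary that is kept, and present it as supplementary;
5. state that the second questionnaire is taken at first closure or Week 12, so its timing depends on outcome, and that baseline adjustment does not remove this.

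Keep the list of named scores short, since each brings its own interval with no multiplicity control. The cost is wording and some scoring and programming. No visits, patients or data are added, because both questionnaires are already scheduled. The change should be made before any SF-36 data are summarised by arm.

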#### Cost effectiveness / Economic model (Amount of product usage, length of treatment)

Results will be summarized descriptively by timepoint where applicable.

### **7.7. Adverse Events**

#### **7.7.1. All Adverse Events**

Summaries of incidence rates of individual AEs overall will be prepared. Only treatment emergent AEs will be analyzed (a treatment emergent adverse event is one that started or worsened in severity at or after start of randomized treatment). Because a patient may experience more than one AE, summaries will provide both the number of patients experiencing at least one event and the number of events within a reporting period. Percentages provided will be the percent of patients experiencing one or more adverse events. In addition, incidence of AEs will be presented by severity (mild,

moderate, severe) and by relationship to investigational product or procedure. Patients experiencing an event more than once will be counted under the maximum severity/relationship experienced.

A listing of all adverse events will include the patient number, AE number, days since index procedure, the AE name, the severity of AE, whether or not the AE is classified as serious (SAE), the relationship of the AE to the study product or procedure, the action taken, and the outcome.

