At the end of the 12-week treatment period, complete wound closure occurred in 75.0% (18/24) of patients who received synthetic hybrid-scale fiber matrix. The average wound area reduction over 12 weeks was 96%, and the average time to complete wound closure was 6.4 weeks. A significant increase in epithelialization was observed from the initial to the final assessment ( $p<0.0001$ , Wilcoxon matched-pairs signed rank test), with nearly complete covering seen at final assessment. This was paralleled by a significant decrease in the amount of wound exudate ( $p<0.0001$ ) to a nearly dry wound at the final assessment, and complete disappearance of necrotic tissue over time ( $p=0.0001$ ). An average of 4.3 scaffolds were used per patient over the treatment period. Fixation was used to hold all scaffolds in place, with the most popular fixation technique being the use of Steri-Strips. The decision of the frequency of re-application was solely at the discretion of the clinician who was treating the wounds, and results found that half of the patients received reapplication of the nanofiber matrix on a weekly basis, whereas the other half of the patients had less frequent re-application rates. Neither fixation technique nor application frequency were found to have a statistically significant effect on

complete wound closure ( $p=0.41$ , Chi-square test and  $p=0.64$ , Fisher's exact test, respectively). In total, the clinical results suggest that synthetic hybrid-scale fiber matrix offers a new and unique alternative in the treatment of chronic DFUs and assists in properly powering an expanded multi-center randomized controlled clinical trial.

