## **5.13. Study Exits**

### **5.13.1. Study Participation Exit Points**

A patient's participation in the study will end after any of the following:

- Patients with complete re-epithelialization and closure confirmation
- Patients without complete re-epithelialization at 12 weeks
- Patient withdrawal
- Patient lost to follow-up
- Amputation of all or part of the study limb
- Closure of study
- Patient death

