### **6. ADVERSE EVENT**

#### **6.1. Principal Investigator Responsibilities**

The investigator (or designee) should record and maintain all adverse events that occur over the course of the patient's participation in the study (randomization through study exit) during or outside of study visits. Adverse events that are reported to the sponsor will be assessed by an investigator. Adverse event assessments should include severity, seriousness, and relatedness to the product, study procedures and pre-existing conditions. See Section 6.4 for adverse events that are required to be reported to the Sponsor.

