#### **7.7.2. Serious Adverse Events**

Summaries of incidence rates and relationship to the study product/procedure of individual SAEs will be prepared. Summaries will provide both the number of patients and the number of events within a reporting period. Percentages provided will be the percent of patients experiencing one or more serious adverse events. A data listing of SAEs will also be provided, displaying details of the event(s) captured on the CRF.

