#### **7.7.3. Adverse Events of Interest**

Summaries of incidence rates of the following AEs by treatment group will be prepared:

- Infection of wound and/or area surrounding wound
- Amputation of lower extremity
- Allergic reaction
- Excessive redness, pain, swelling or blistering of wound

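### AE summaries make no allowance for observation time, although AE follow-up ends sooner for patients whose wounds heal early

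*Combined protocol and SAP*

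**What the plan says.** On collection, section 6.1 has the investigator record AEs over the whole of participation, "randomization through study exit". Section 5.13.1 lists the exit points. One is "Patients with complete re-epithelialization and closure confirmation"; another is the 12-week point for patients whose wound has not closed. Appendix A, note 2, places the confirmation visit two weeks (± 3 days) after closure is first seen, with an AE check, and does not require it of patients who have not closed by week 12.

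On analysis, 7.7.1 states that "summaries will provide both the number of patients experiencing at least one event and the number of events within a reporting period", and then: "Percentages provided will be the percent of patients experiencing one or more adverse events". The reporting period is not defined. Section 7.7.2 also gives patients and events, and adds: "Percentages provided will be the percent of patients experiencing one or more serious adverse events". Section 7.7.3 reads: "Summaries of incidence rates of the following AEs by treatment group will be prepared". Section 7.5 says that all results are presented by treatment group. The AE listing in 7.7.1 includes days since the index procedure. No section plans person-time, an exposure-adjusted rate, time to first AE, or an observation window common to all patients.

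The protocol summary (section 1) describes a different window: AE assessment weekly until re-epithelialization or week 12, whichever comes first.

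**The concern.** The length of AE observation is set by the primary efficacy outcome. A patient who closes at week 6 is watched for about 8 weeks; one who never closes is watched for 12. If one arm heals more wounds, or heals them earlier, its patients have less time in which an AE can be recorded. Percentages of patients and raw event counts both fall with shorter observation, so part of an efficacy difference can pass into the safety table as an apparent safety difference. A reader of the planned tables could not see this, because they show no observation time by arm.

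**Working it through.** The plan gives no figure for AE observation time, so there is none to reproduce. The check builds one from the plan's own inputs.

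**Inputs from the documents**
- Closure by week 12: 80% Restrata, 40% control (7.3).
- Time to closure: in the single-arm pilot of the product, "the average time to complete wound closure was 6.4 weeks" (2.1).
- Exit: closure plus about 2 weeks for closers, week 12 for non-closers (5.13.1, Appendix A note 2). Sections 5.12 and 7.6.1 put the confirmation visit within 2 weeks; 2 weeks is used here.
- 24 patients per arm (section 1).

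**Assumptions not in the documents**
- Control patients who close do so at 6.4 weeks on average, or at week 9 as an alternative.
- Weekly AE risk is constant and equal in the arms, giving 20% (or 40%) incidence over 12 weeks.
- All closers in an arm close at that arm's mean week, and there is no dropout.

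**Step 1: expected observation.** With closure proportion p and mean closure week T, weeks = p × (T + 2) + (1 − p) × 12.
- Restrata: 0.8 × 8.4 + 0.2 × 12 = 9.12.
- Control, T = 6.4: 0.4 × 8.4 + 0.6 × 12 = 10.56; ratio 9.12/10.56 = 0.86.
- Control, T = 9: 0.4 × 11 + 0.6 × 12 = 11.6; ratio 9.12/11.6 = 0.79.

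**Step 2: crude percentages under equal risk.** For 20% over 12 weeks, h = −ln(0.8)/12 = 0.0186 per week. The chance of at least one AE is 1 − exp(−8.4h) = 14.5% for a closer at 6.4 weeks, 1 − exp(−11h) = 18.5% for a closer at week 9, and 20% for a non-closer.
- Restrata: 0.8 × 14.5% + 0.2 × 20% = 15.6%.
- Control: 0.4 × 14.5% + 0.6 × 20% = 17.8%, or 0.4 × 18.5% + 0.6 × 20% = 19.4%.
- Gap 2.2 to 3.8 points; apparent relative risk 0.88 to 0.80 where the true weekly risk is equal.

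At 40% over 12 weeks the same steps give 32.1% against 36.0% to 39.0%, a gap of 4.0 to 6.9 points.

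**Step 3: size against sampling error.** With 24 per arm, the SE of the difference in the 20% case is √(0.156 × 0.844/24 + 0.178 × 0.822/24) = 10.8 points (11.0 with 19.4% in control). The expected gap is 0.022 × 24 = 0.5 to 0.038 × 24 = 0.9 of a patient. Comparing two binomial counts with these percentages, Restrata shows the lower figure in about 50% to 56% of trials and the higher in about 29% to 34%; the rest are ties.

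**Step 4: direction.** The formula in step 1 rearranges to 12 + p × (T − 10). At T = 10 in both arms, observation is 12.0 weeks in each. At T = 11 it is 12.8 (Restrata) against 12.4 (control), because late closers are followed to week 13 or 14 and non-closers only to week 12. With Restrata at 6.4 weeks, control observation falls below 9.12 only if 0.4 × (T − 10) < −2.88, that is, if control closers average earlier than week 2.8.

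**Step 5: the protocol summary's window.** Without the extra 2 weeks, Restrata has 0.8 × 6.4 + 0.2 × 12 = 7.52 weeks. Control has 0.4 × 6.4 + 0.6 × 12 = 9.76, or 0.4 × 9 + 0.6 × 12 = 10.8. The ratio becomes 0.77 to 0.70, so the imbalance depends on which window applies.

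**The case against.** A reader might infer three stronger things, and the documents support none of them.

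- *That AEs are reported only as percentages of patients.* Sections 7.7.1 and 7.7.2 also give event counts, and the listing gives AE timing. The counts do not cure the problem, since under equal risk they shrink by the same exposure ratio, but the plan is not limited to percentages.
- *That Restrata will look safer.* Step 3 shows a shift well inside sampling error, with the opposite ordering in roughly three trials in ten. Step 4 shows that the direction depends on closure timing. The 6.4 weeks comes from a single-arm study of the product; the documents give no closure time for controls.
- *That an exposure-adjusted rate should replace the percentages as the basis of a safety statement.* The rate is neutral only if risk is roughly constant. If AEs cluster early and equally in both arms, dividing by unequal time gives a false rate ratio against Restrata of about 10.56/9.12 = 1.16 to 11.6/9.12 = 1.27. Two of the four AEs of interest in 7.7.3 concern the wound itself, and their risk may fall once it closes. Fewer wound infections because wounds close sooner would be a treatment effect, not an artefact.

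It is also fair to say that AE incidence is a tertiary outcome and that 7.7 plans summaries and listings with no test. In addition, 6.4 requires AE forms only for serious, product- or procedure-related, or listed events, so a rate for all AEs may not be obtainable.

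These points limit the claim and the remedy. They do not remove the core: observation time depends on healing, the plan does not show it, and the expected shift does not shrink as the sample grows.

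**Conclusion.** The concern holds as a modest, correctable weakness in the descriptive safety tables. On the plan's closure rates and the pilot's closure time, Restrata patients would be observed for about 14% to 21% less time than controls (ratio 0.86 to 0.79). Equal weekly risk would then show as a difference of about 2 to 4 points at 20% incidence over 12 weeks. That rests on a constant and equal risk, no dropout, and an assumed closure time for controls, none of which the documents establish. The shift is an expectation, smaller than sampling error at 24 per arm, and it favours the faster-healing arm only if closures come before about week 10 on average. The mismatch between the AE window in the protocol summary and that in section 6.1 and Appendix A is a separate inconsistency that needs settling in any case.

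**What to change.** In 7.7.1 to 7.7.3, add by arm, beside the crude percentages and event counts:
- the total patient-weeks of AE observation;
- the number of patients with a first event per 100 patient-weeks at risk, with a 95% CI.

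Do this for AEs reportable under 6.4, for SAEs, and for each AE of interest. Start the clock at the start of randomized treatment, to match the treatment-emergent definition in 7.7.1, and stop it at the first event or the end of AE observation. State that the percentages and rates are read together, and that the rate is not the sole basis for any safety statement.

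Reconcile the AE window in the protocol summary (to re-epithelialization or week 12) with section 6.1 and Appendix A (to study exit), since the denominator cannot be defined until one window applies.

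The cost is SAP wording and one extra column per table, using randomization, event and exit dates that the study already needs. The downside is that the rate assumes a roughly constant risk over time, which should be said in a footnote.
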